3.1 Background on Telotristat Ethyl (XERMELO®) and Carcinoid Syndrome (CS)

Well differentiated neuroendocrine tumor (NET), formerly known as carcinoid tumor, is a relatively rare tumor type that arises from cells of the neuroendocrine system (Kulke, 2011; Turaga, 2011; Yao 2008).

Carcinoid syndrome (CS) occurs when well differentiated NETs secrete large amounts of serotonin and other vasoactive products into the systemic circulation. By one estimate, CS develops in approximately 10% of adult patients with well differentiated NET and, with a few exceptions, only manifests itself in the presence of liver metastasis (Tomassetti, 2001). By another estimate, approximately 8% to 35% of patients with NET have associated CS, with tumors of the small intestine carrying the highest risk (Rorstad, 2005). Classically, symptoms associated with CS include flushing, diarrhea, wheezing, abdominal pain, and valvular heart disease, although, a variety of other symptoms can occur. Roughly 75% of patients with CS experience diarrhea, which can occur either with or without other manifestations of the syndrome, and has perhaps the most direct impact on activities of daily living (Moertel, 1987).

Valvular heart disease has been associated with high serotonin levels (as measured by its metabolite, urinary 5-hydroxyindoleacetic acid [u5-HIAA]). Due to the slow growing nature of NETs and the prolonged course of disease, about 50% of patients with CS will eventually develop heart disease. Usually only metastatic NETs result in pathological changes to the heart as a result of the hypersecretion of vasoactive substances; in these cases, the development of cardiac pathology heralds a more precipitous decline in clinical course (Fox, 2004; Gustafsson, 2008; Turaga, 2011).

In epidemiological studies, high levels of u5-HIAA in patients with NETs have been associated with poor survival. van der Horst Schrivers, et al prospectively studied 76 patients with midgut well differentiated NETs (van der Horst Schrivers, 2007). Urine collected over a 24 hour period every 3 months was tested for u5 HIAA levels. Patients with high u5-HIAA levels (>20 mmol/mol creatinine) had a median survival of 33 months compared with 90 months for patients with a moderately high level (≤ 20 mmol/mol creatinine) (hazard ratio=3.33; 95% confidence limit [CL]: 1.66-6.66; $p=0.001$) (Turaga, 2011).

Morbidity Associated with Carcinoid Syndrome

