Common side effects of SSAs are back pain, fatigue, headache, abdominal pain, nausea, and dizziness. Other side effects identified include biliary tract abnormalities (jaundice, gallstones, sludge, and dilatation), hyper- or hypoglycemia, hypothyroidism, and cardiac changes (sinus bradycardia, conduction abnormalities, and arrhythmias) (Novartis Pharmaceuticals Corp., Sandostatin® LAR Depot package insert, 2016).

Recently, results from the PROMID and CLARINET studies demonstrated the antiproliferative effects of octreotide and lanreotide autogel® (Caplin, 2014; Rinke, 2009).

Therefore, use of SSAs to reduce tumor proliferation has become increasingly common in the treatment paradigm for many patients with NET with or without symptoms.

In a substantial number of NET patients with CS, a tachyphylaxis to SSA treatment may occur as soon as 1 week and as long as 12.5 months after starting therapy (Garland, 2003; Moertel, 1987), possibly due to desensitization of the SSAs' effect on the somatostatin receptors (Hofland, 2003). This desensitization to SSAs may be overcome in some patients by increasing the dosage of SSA above the approved label; however, the efficacy and safety of higher doses is not yet established (Broder, 2015). Significant tumor progression might also contribute to the decrease in efficacy of SSAs over time.

Patients whose symptoms are generally controlled using long-acting SSA therapy may require supplemental doses of short acting SSA therapy when symptoms become exacerbated. Results of a 93 patient study with octreotide indicate approximately 35% to 40% of the patients who received the long-acting release (LAR) Depot formulation still require supplemental subcutaneous (rescue) therapy to control exacerbation of CS symptoms. After 6 months of treatment with octreotide, the number of patients requiring "rescue" doses increased to approximately 50% to 70% of patients. When a patient's response to SSA therapy declines, it is accepted practice to continue SSA therapy while initiating additional treatments, including additional prescribed and over the counter medications (Öberg, 2004).

Surgical debulking of tumors, radiation, various liver directed therapies, and chemotherapy may be attempted as a way of addressing overall tumor burden and reducing associated serotonin production (Kulke, 1999; Kulke, 2011; Öberg, 2012; Turaga, 2011).

Scientific Background for Development of XERMELO

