3.2 Rationale for Current Study

This observational study will capture patient experience with XERMELO in a real-world setting. XERMELO is the first orally available drug to be indicated for the treatment of CS diarrhea.

The clinical development program provided experience in more than 200 patients with CS and demonstrated statistically significant reductions in daily BM frequency, as well as an acceptable safety and tolerability profile. Data from 2 clinical studies, TELESTAR and TELECAST, support that the mechanism of action for XERMELO holds an important role in the treatment of CS. By reducing the production of peripheral serotonin, XERMELO is able to significantly reduce the frequency of CS diarrhea.

Patient satisfaction with XERMELO was not thoroughly studied in the clinical program and is not readily available in medical records. Results of a 35-patient interview sub-study conducted in TELESTAR after 12 weeks of blinded treatment indicated that nearly all patients reporting reductions in BM frequency during the Double-blind Treatment Period described them as meaningful, allowing them to better enjoy life and participate more in social and physical activities. Among interview participants (n=33) answering the question about satisfaction with the ability of the blinded study drug to treat CS, 50% of patients (12/24) on active treatment reported “very satisfied” while 0 patients in the placebo group reported the same term. The Sponsor assumes that satisfied patients will continue XERMELO to avoid the complications of CS, leading to better long-term outcomes ([Lexicon Pharmaceuticals, Inc., Clinical Study Report, 2017](#)).

Real-world experience with pharmaceutical products may only be evaluated once the product is available within the marketplace. In capturing patient experience, this study will also assess the patient journey though medical diagnosis of NET and treatment for CS in the clinical setting.

4. Study Objectives

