3.2.5 Work Productivity and Activity Impairment Questionnaire—Specific Health Problem (WPAI-SHP)

The WPAI-SHP is a self-administered questionnaire ([Reilly et al., 1993](#)) comprising 6 questions that measure the effect of health problems on participants' ability to work and participate in regular activities based on their experiences in the previous 7 days. This questionnaire will be administered at Baseline and at the initial 6-month Follow-up.

The WPAI-SHP includes 4 domains (absenteeism, presenteeism, work productivity loss, and activity impairment). All participants will be asked whether they are employed (Q1) and how their CS-related problems affected their regular activities (Q6). Employed participants will be asked about hours of work missed due to CS-related problems (Q2), hours of work missed for any reason (eg, vacation, holidays, time off to participate in this study) (Q3), hours actually worked (Q4), and the degree that CS affected their productivity while working (Q5). An integer scale from 0 to 10 is used for Q5 and Q6, where 0 corresponds to no effect and 10 corresponds to complete effect.

Responses to the items are scored to produce the following 4 domains:

- Absenteeism: work time missed due to CS = [REDACTED]
- Presenteeism: impairment while working due to CS = [REDACTED]

- Work productivity loss: overall work impairment due to CS = [REDACTED]
[REDACTED]
- Activity impairment: activity impairment due to CS = [REDACTED]

Each score is then multiplied by 100 to express domains in terms of impairment percentages, with higher numbers indicating greater impairment and less productivity (ie, worse outcomes).

3.2.6 *Carcinoid Syndrome-related Health Care Resource Utilization*

At Baseline and at each Follow-up, questionnaire items will ask patients about ER visits and hospitalizations during the prior 6-month period. Data collected will include the following:

- The number of ER visits and the CS-related reason for each visit
- The number of hospitalizations, the number of nights for each stay, and the CS-related reason for each hospitalization

3.2.7 *Study Discontinuation and Mortality*

Patients will be terminated from the study if they discontinue the use of XERMELO, withdraw consent for participation, or are lost to follow-up. Information on reasons for discontinuation will be provided by the specialty pharmacy.

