5.1.5.4 Exploratory Analyses

Exploratory analysis of the association between patient satisfaction with overall CS symptom control at the initial 6-month Follow-up and the incidence of at least 1 ER visit, at least 1 hospitalization, and mortality will be performed as part of the final analysis. Only patients with non-missing data on satisfaction with overall CS symptom control at 6 months

will be included in the analysis. The satisfaction categories correspond to the binary categories used in the main analysis of the primary endpoint.

- Contingency table analysis to compare the incidence proportions of ER visits, hospitalizations, and mortality for each Follow-up interval and for the entire study period by satisfaction category, with chi-square tests for association. The satisfaction categories correspond to the binary categories used in the primary endpoint.
- Logistic regression models for the incidence of at least 1 ER visit and/or at least 1 hospitalization during the study period, with satisfaction category as a predictor variable. Covariates may be included in the models.

Additional or alternative exploratory analyses to be performed after data collection is complete will be determined in consultation with Lexicon and described in the final study report. The feasibility of each additional analysis will depend on the extent of data availability. Examples of additional analyses that may be considered are as follows:

- Kaplan-Meier analysis of mortality data, stratified by satisfaction category, including log-rank tests for differences between the strata.
- Kaplan-Meier analysis of time to first hospitalization, first ER visit, or mortality.
- Cox models for times to first ER visit, first hospitalization, and mortality, with satisfaction category as a predictor variable. Covariates may be included in the models.

Statistical tests will be 2-sided and have an associated alpha level of 0.05. The p-values from these tests will be considered descriptive rather than inferential.

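### The satisfaction–outcome association in SAP 5.1.5.4 has no committed baseline adjustment and counts events that precede the month-6 rating

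*SAP*

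**What the plan says.** SAP 5.1.5.4 splits patients with a month-6 answer into satisfied and not satisfied, and commits to two analyses.

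- Contingency tables of ER visits, hospitalizations and mortality "for each Follow-up interval and for the entire study period by satisfaction category, with chi-square tests for association".
- "Logistic regression models for the incidence of at least 1 ER visit and/or at least 1 hospitalization during the study period", with satisfaction category as predictor. On adjustment the SAP says only "Covariates may be included in the models"; it names no covariate and no selection rule.

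Mortality has no committed model. Kaplan-Meier and Cox analyses are listed as examples that might be considered. "Statistical tests will be 2-sided and have an associated alpha level of 0.05", and the p-values are labelled descriptive.

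Protocol 3.2 gives the idea behind the comparison: "The Sponsor assumes that satisfied patients will continue XERMELO to avoid the complications of CS, leading to better long-term outcomes". Protocol 10.4.1 leaves it to the SAP to describe the models and their appropriateness or limitations. SAP 5.1.5.4 names models but gives no limitation on how the association may be interpreted.

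Baseline data bearing on disease burden are already collected. On health care use, SAP 3.2.6 says: "At Baseline and at each Follow-up, questionnaire items will ask patients about ER visits and hospitalizations during the prior 6-month period". Baseline also records overall satisfaction (SAP 3.2.3), diagnosis dates, NET site and recent NET surgery (SAP 3.2.1 and 3.2.2), and systemic and liver-directed therapy (Protocol 5.1.1 and 8.2.2.4).

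**The concern.** There are two separate problems.

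**Confounding.** Protocol 3.1 attributes the syndrome to serotonin secretion. It reports that patients with high u5-HIAA "had a median survival of 33 months compared with 90 months for patients with a moderately high level", says severe diarrhea can lead to complications such as electrolyte imbalance and malnutrition, and notes that "Significant tumor progression might also contribute to the decrease in efficacy of SSAs over time". On that account, patients with heavier disease could well be both less satisfied at month 6 and more often hospitalized or dead. A crude comparison would then favour satisfied patients whatever satisfaction does.

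**Timing.** The month-6 survey asks about the preceding 6 months, so the first follow-up interval ends when satisfaction is rated. A hospitalization in month 3 can lower the month-6 rating, yet it counts as an outcome in the whole-period tables and models. This affects ER visits and hospitalizations. A death before the rating leaves no satisfaction answer, so that patient is not in the analysis.

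At stake is the interpretation of the exploratory objective. A crude odds ratio below 1 would look like support for the sponsor's assumption when it might reflect only baseline severity or early events.

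**Working it through.** **The plan's own figures.** The documents give no figure for this association. The sample size in SAP 2.4 supplies the number of month-6 responders: 1.96² × 0.5 × 0.5 / 0.05² = 384.1, rounded up to 385. With 40% dropout, 385 / 0.6 = 641.7, or 642 against the stated 643, an immaterial difference. I use n = 385 below.

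**Confounding, illustrated for death.**

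Inputs from Protocol 3.1: median survival of 33 months (severe) and 90 months (less severe). Assumptions: exponential survival, half of patients in each stratum, 30 months from month 6 for everyone, and no effect of satisfaction.

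- Death risk, severe: 1 − 2^(−30/33) = 0.4675
- Death risk, less severe: 1 − 2^(−30/90) = 0.2063

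The implied hazard ratio is 90/33 = 2.73. The protocol reports 3.33 (95% CL 1.66–6.66).

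Let a be the proportion satisfied among less severe patients and 1 − a among severe patients. Then:

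- risk if satisfied = a × 0.2063 + (1 − a) × 0.4675
- risk if not satisfied = (1 − a) × 0.2063 + a × 0.4675

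For a = 0.65: 0.1341 + 0.1636 = 0.298 and 0.0722 + 0.3039 = 0.376. OR = (0.298/0.702) / (0.376/0.624) = 0.70.

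| Gap (points) | Satisfied: less severe / severe | Risk, satisfied | Risk, not satisfied | Crude OR | Chi-square p < 0.05 (n = 385) |
|---|---|---|---|---|---|
| 0 | 50% / 50% | 0.337 | 0.337 | 1.00 | 5% |
| 10 | 55% / 45% | 0.324 | 0.350 | 0.89 | 8% |
| 20 | 60% / 40% | 0.311 | 0.363 | 0.79 | 18% |
| 30 | 65% / 35% | 0.298 | 0.376 | 0.70 | not run |
| 40 | 70% / 30% | 0.285 | 0.389 | 0.62 | 60% |

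The last column comes from 2,000 simulated studies per row.

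**Sensitivity** (gaps of 10, 20 and 40 points).

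- 30% severe: OR 0.90, 0.81, 0.65.
- Half severe, 12 months of follow-up: 0.90, 0.81, 0.66.
- 80% severe, 20-point gap only: 0.87.
- ER visit or hospitalization, with assumed risks of 40% (severe) and 20% (less severe), half severe: 0.91, 0.83, 0.68.

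**What adjustment achieves** (same simulations, death). Adjusting for severity measured without error returns the OR to 1.00–1.01 and rejection to 4.4–5.2%. Adjusting for a proxy that classifies 80% of patients correctly gives OR 0.93, 0.86 and 0.72, with rejection of 6%, 10% and 31%, for gaps of 10, 20 and 40 points.

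**Early events** (all inputs assumed). Suppose 10% of patients have an event in months 0–6, of whom 40% are satisfied, against 52% of the rest. The later event risk is 30%, unrelated to satisfaction.

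- Satisfied: (0.10 × 0.40 + 0.90 × 0.52 × 0.30) / 0.508 = 0.355
- Not satisfied: (0.10 × 0.60 + 0.90 × 0.48 × 0.30) / 0.492 = 0.385
- OR = 0.88

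With 20% having an early event, and 30% against 55% satisfied, the same formula gives 0.384 and 0.496, OR 0.63.

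**The case against.** The strongest reply is that the plan claims association only. The objective is exploratory, all analyses are called descriptive, and covariates are already allowed. This stands as a limit on importance. But a descriptive label on p-values deals with error rate, not bias: the odds ratio is confounded whether or not a p-value accompanies it. Permission to adjust also leaves the choice of covariates until after results are seen.

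A reader might infer that the protocol makes severity a cause of both satisfaction and outcome, so that a protective association is to be expected. The documents do not support that. Protocol 3.1 reports severity and survival as an association and never mentions satisfaction in that context. Its remark on tumor progression concerns SSAs and is hedged. SAP 3.2.3 says the month-6 item asks how XERMELO has controlled symptoms, which is closer to drug response than to disease burden. With no satisfaction gap by severity, this bias is zero.

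The inputs also deserve caution. The medians come from a study of 76 midgut NET patients, not from CS patients starting XERMELO. The 50/50 split has no source. Thirty months is the maximum: the last patients enrolled may have only the month-6 survey (Protocol 6), and stopping XERMELO ends participation (SAP 3.2.7). The death risks are therefore upper-end figures, though the 12-month odds ratios are similar. The main table also concerns death, which the quoted logistic model does not cover.

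The missing mortality model might be read as an oversight. SAP 3.2.7 gives a reason: deaths may arrive only as counts per interval. The request for a mortality model must be conditional on patient-level data.

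**Conclusion.** The concern holds in limited form. Followed exactly, SAP 5.1.5.4 can report only crude associations, and for ER visits and hospitalizations it mixes events before and after the rating. A protective association with no effect of satisfaction is plausible, not demonstrated. Under the stated assumptions the crude OR for death runs from 1.00 with no gap to 0.62 at 40 points, and the gap itself is unknown. Early events could push the ER and hospitalization results in the same direction.

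It would also be too strong to infer that baseline adjustment cures this. u5-HIAA is not collected, and imperfect proxies remove only part of the bias. The case for change is that a better analysis is available from data already planned, and that Protocol 10.4.1 calls for the SAP to describe the appropriateness or limitations of its models.

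**What to change.** In SAP 5.1.5.4:

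1. Make the main association analysis a model of events after the month-6 survey on satisfaction category. Adjust at least for any CS-related ER visit or hospitalization in the 6 months before Baseline and for baseline overall satisfaction.
2. If event numbers allow, add time since NET diagnosis and baseline systemic or liver-directed therapy or NET surgery.
3. Fit the same adjusted model for mortality if patient-level deaths are available.
4. Keep the chi-square tables as unadjusted description, either restricted to intervals after month 6 or with months 0–6 shown separately.
5. State that residual confounding remains because u5-HIAA is not collected, and that the result is not an effect of satisfaction or of staying on XERMELO.

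The cost is SAP wording and a few covariates already in the Baseline survey. Patients with missing baseline items, or with no follow-up beyond month 6, drop out of the model. The reported association is likely to be weaker.

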10.4.1 Analyses of Study Endpoints

For the primary endpoint, the proportion of CS patients who are at least somewhat satisfied with their overall symptom control at 6 months, a point estimate and the corresponding 95% CLs will be calculated. Secondarily, a point estimate and corresponding 95% CLs will be calculated for the proportion of CS patients who are very satisfied with their overall symptom control at 6 months. The 95% CLs will be unadjusted and based on the assumption of approximate normal distribution. Missing data will not be imputed in the main analysis of the primary endpoint. As a sensitivity analysis, a patient with a missing response at 6 months will be imputed as a non-responder. This approach corresponds to non-responder imputation.

In addition to the point estimates and 95% CLs for the primary endpoint, the frequency distribution of the categorical responses, on a 5-point Likert scale, to patient satisfaction with overall symptom control at 6 months will be presented. The patient satisfaction measure will also be summarized as an ordinal variable with a value of 1 corresponding to “very dissatisfied” up to 5 corresponding to “very satisfied”.

All the secondary endpoints correspond to proportions and will be summarized through point estimates and 95% CLs, as described above for the primary endpoint. Frequency distributions of the categorical responses and summary statistics of the corresponding ordinal values of the categories will be presented. The handling of patients with a response of “not applicable” to patient satisfaction with CS-related diarrhea control or patient satisfaction with CS-related flushing control in the analysis will be described in the SAP.

The 4 WPAI-SHP scores at Baseline and month 6 will be summarized, as well as the change from Baseline to month 6.

The incidences of at least 1 CS-related hospitalization, at least 1 CS-related ER visit, and mortality after Baseline will be calculated at each 6-month interval. Kaplan-Meier estimates of each time-to-event variable, including quartiles, medians, and their corresponding 95% CLs, will be presented. The association or relationship between the primary endpoint and each long-term health outcome will be evaluated through descriptive statistics and the use of statistical models, as appropriate. Any statistical models that will be used and the appropriateness and/or limitations of their use will be described in the SAP.

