2.2.2 Secondary Objectives

The following secondary objectives will be assessed 6 months after initiating treatment with telotristat ethyl (XERMELO):

- To estimate the proportion of patients reporting satisfaction of CS-related diarrhea control
- To estimate the proportion of patients reporting satisfaction of CS-related flushing control
- To estimate the proportion of patients reporting reduction in rescue SSA use

- To estimate the proportion of patients reporting reduction in the dose of long-acting SSA injection
- To estimate the proportion of patients reporting reduction in the frequency of long-acting SSA injection
- To estimate the proportion of patients reporting an overall improvement in CS control after initiating XERMELO based on the Patient Global Impression of Change (PGIC)
- To estimate the proportion of patients who had reduction in work-related absenteeism, presenteeism, activity impairment, and overall productivity loss after initiating XERMELO based on Work Productivity and Activity Impairment Questionnaire: Specific Health Problem v.2.0 (WPAI-SHP)
- To estimate the proportion of patients reporting weight gain

2.2.3 *Exploratory Objectives*

To explore the association between satisfaction with overall and CS symptom control (ie, diarrhea, flushing) at month 6 and long-term health outcomes such as, CS-related hospitalization, CS-related emergency room (ER) visits, and mortality over the study period

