5.1.5 Other Endpoint Analyses

5.1.5.1 Analyses of Incidence of Emergency Room Visits, Hospitalizations, and Mortality

Incidence proportions for patients with at least 1 ER visit, at least 1 hospitalization, and mortality during each 6-month Follow-up interval will be reported along with 95% CLs. The denominator for each incidence proportion will be the number of patients enrolled in the

study at the beginning of that particular 6-month interval who also provide a non-missing response to the questionnaire item for each type of event.

The time to the first occurrence of a CS-related ER visit, time to the first occurrence of a CS-related hospitalization, time to the first occurrence of a CS-related ER visit or hospitalization, and time to mortality will be analyzed using the nonparametric Turnbull estimation method ([Turnbull, 1976](#)) for interval-censored data available in SAS PROC ICLIFETEST for each 6-month interval during Follow-up. These tables will display the number of patients still at risk at the beginning of the interval along with the number of events and censored observations within each interval. Estimates of the survival probability (the proportion of patients without the event) will be provided for the upper boundary of each interval, and these probabilities will also be displayed as figures. Estimated quartiles for event-free time (with 95% CLs) will be reported.

If death dates are available for the analysis of mortality, this analysis will be performed using the Kaplan-Meier method instead of the Turnbull method. Estimated quartiles for survival time (with 95% CLs) will be reported, and estimated survival probabilities will be displayed as Kaplan-Meier curves.

Details for all ER visits and hospitalizations, including the reason for the visit or hospitalization, will be provided in data listings.

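### The named satisfaction-outcome analyses in SAP 5.1.5.4 make no use of the collected event counts, and the whole-period logistic model names no adjustment for unequal follow-up; a rate model with a follow-up offset should be pre-specified beside it

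*SAP*

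**What the plan says.** SAP 3.2.6 sets out the collection: "At Baseline and at each Follow-up, questionnaire items will ask patients about ER visits and hospitalizations during the prior 6-month period". The items are "The number of ER visits and the CS-related reason for each visit" and "The number of hospitalizations, the number of nights for each stay, and the CS-related reason for each hospitalization".

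The exploratory objective (SAP 2.2.3) is "To explore the association between satisfaction with overall and CS symptom control (ie, diarrhea, flushing) at month 6 and long-term health outcomes", these outcomes being CS-related hospitalization, CS-related ER visits and mortality.

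The analyses named for these data are:
- Protocol 10.4.1: "The incidences of at least 1 CS-related hospitalization, at least 1 CS-related ER visit, and mortality after Baseline will be calculated at each 6-month interval".
- SAP 5.1.5.1: "Incidence proportions for patients with at least 1 ER visit, at least 1 hospitalization, and mortality during each 6-month Follow-up interval", and Turnbull estimates that begin with "The time to the first occurrence of a CS-related ER visit, time to the first occurrence of a CS-related hospitalization".
- SAP 5.1.5.4: chi-square tables by satisfaction category, for each follow-up interval and for the whole study; then "Logistic regression models for the incidence of at least 1 ER visit and/or at least 1 hospitalization during the study period", with satisfaction as predictor and covariates optional. Kaplan-Meier and Cox analyses of first events and death are listed only as examples that may be considered.

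On follow-up, Protocol section 6 follows each patient for up to 3 years, but the last patient enrolled can complete only the Baseline and first 6-month surveys. Protocol 5.1.1 and SAP 3.2.7 end participation when XERMELO is stopped. Protocol 3.2 records the sponsor's assumption that satisfied patients will continue XERMELO.

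**The concern.** There are two related problems, both on the outcome side of the association.

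First, in the whole-period chi-square and logistic analyses a patient with several admissions counts the same as a patient with one. The time-to-first-event analyses also ignore everything after the first event. Where repeat events are common, they carry much of the information on whether satisfied patients use less hospital care. As follow-up lengthens, more patients in both groups reach one event and the binary outcome discriminates less.

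Second, the chance of at least one event grows with time observed. The whole-period logistic model names no term for that time, and observation stops with treatment. If satisfaction keeps patients on treatment, satisfied patients are watched longer and have more opportunity to record an event. The comparison then mixes event rate with length of observation.

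**Working it through.** **The plan's own figure.** SAP 2.4: 1.96² × 0.5 × 0.5 / 0.05² = 384.2, rounded up to 385 month-6 responders. With 40% dropout, 385 / 0.6 = 641.7, so 642 against the stated 643, a difference of no consequence. Neither document gives an event rate, a dispersion or a power figure for the utilization analyses.

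**Inputs.** From the SAP: 385 patients with a month-6 answer, a 50% expected proportion satisfied (used here as the group split: 192 and 193), two-sided alpha 0.05. Assumed: negative-binomial counts with mean μ and dispersion k (k = 0 is Poisson), equal follow-up, and a rate ratio of 0.7 for satisfied against not satisfied.

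**Information kept by the binary outcome.** With P₀ = (1 + kμ)^(−1/k), or e^(−μ) when k = 0, the efficiency of at-least-one relative to the count is [μ/(1 + kμ)] × P₀/(1 − P₀). For μ = 0.5 and k = 1: (0.5/1.5) × (0.667/0.333) = 0.67, a loss of 33%.

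**Power.** Let μ₀ be the mean in the unsatisfied group and μ₁ = 0.7μ₀. For the count, Var(log RR) = (1/μ₀ + k)/192 + (1/μ₁ + k)/193. For μ₀ = 0.5 and k = 1 this is 3/192 + 3.857/193 = 0.0356, so SE = 0.189. Then |ln 0.7|/SE = 0.357/0.189 = 1.89, and power is Φ(1.89 − 1.96) = 47%. For the binary outcome the proportions are 1 − 1/1.5 = 33.3% and 1 − 1/1.35 = 25.9%; the two-proportion test has 36% power.

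| Mean events per patient | Information lost, k = 0 to 2 | Power, count (k = 1) | Power, at least one (k = 1) |
|---|---|---|---|
| 0.1 | 5-13% | 16% | 15% |
| 0.3 | 14-29% | 34% | 29% |
| 0.5 | 23-40% | 47% | 36% |
| 1.0 | 42-54% | 65% | 41% |

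A simulation with 1,500 replicates (robust-variance Poisson against chi-square, k = 1) gave 51% against 37% at a mean of 0.5 and 67% against 42% at 1.0.

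**Per-interval tables.** A mean of 0.5 spread evenly over the five intervals after month 6 is 0.1 per interval. Within an interval the loss is then in the 5-13% row.

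**Unequal follow-up.** Assume k = 1, with unsatisfied patients having 0.5 events per year over 1 year and satisfied patients 0.35 per year over 2 years. The rate ratio is 0.35/0.5 = 0.7 in favor of satisfaction. The expected counts are 0.5 and 0.7, so at-least-one is 1 − 1/1.5 = 33% against 1 − 1/1.7 = 41%. The sign has reversed. With k common to both groups this happens once satisfied patients are followed more than 1/0.7 = 1.43 times as long.

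**The case against.** The strongest case for the plan is this. The SAP follows the protocol, which defines these outcomes as incidences. The analyses are exploratory, the p-values are descriptive and there is no power target. SAP 5.1.5.4 allows additional analyses and covariates, so follow-up time could be entered, and the optional Cox models would deal with unequal follow-up by censoring. Counts are recalled over six months and Protocol 5.1.1 accepts estimates, so at-least-one is less exposed to reporting error. Short follow-up after month 6 would push the mean toward the low rows of the table, where little is lost.

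All of this stands, and it limits the importance of the point. It does not remove it. No count or rate model is among the named analyses or the examples, and a model chosen after data collection carries less weight. Protocol 10.4.1 also leaves it to the SAP to discuss the suitability and limits of the models used; SAP 5.1.5.4 does not do so for the logistic model.

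Three stronger readings are tempting, and the documents do not support them:
- A reader might infer that a fixed share of the information, such as 20-55%, is lost. Without an event rate no single range can be stated.
- A reader might infer that every analysis treats six admissions as one. The per-interval proportions and chi-square tables do see repeat events that fall in different intervals, and time-to-first-event analyses keep timing.
- A reader might infer that the volume of use goes unreported. SAP 4.2 plans full questionnaire summaries and SAP 5.1.1 gives means and medians, so counts and nights should appear at each survey, though not by satisfaction.

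**Conclusion.** The point holds as a low-severity improvement to the exploratory analysis. No named satisfaction-outcome analysis uses the event counts, and the whole-period logistic model names no adjustment for follow-up that varies from about 6 months to 3 years.

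The efficiency cost depends on assumed rates. It is negligible near 0.1 events per patient (about 1 power point), about 11 points at 0.5 and about 24 points at 1.0, for a rate ratio of 0.7 and dispersion 1. These figures take all 385 patients with equal follow-up and counts reported without error, so they are likely to be optimistic for the count model. The loss from leaving out nights was not quantified.

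The follow-up problem needs no assumed event rate to exist, but its direction and size depend on how far follow-up differs by satisfaction. The documents support the possibility of a reversed association; they do not show that one will occur.

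**What to change.** In SAP 5.1.5.4, keep the at-least-one logistic model and pre-specify beside it a negative-binomial model (or Poisson with robust variance) for the number of CS-related hospitalizations, the number of CS-related ER visits, and their total. Count events after the month-6 survey, so that the outcome follows the satisfaction answer. Use the main-analysis satisfaction category as predictor and log observed follow-up time after month 6 as offset, and report the rate ratio with 95% CL. Patients with no follow-up after month 6 do not contribute, and their number should be shown.

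The cost is SAP wording and a few extra tables from standard SAS procedures, with no new data or patients. The downside is that patient-reported counts are open to recall error and to a few heavy users; the robust variance and the retained at-least-one result make this visible. The offset corrects for unequal observation time but not for informative dropout, and the SAP should say so.

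Events and nights per patient-year in SAP 5.1.5.1 would be a useful addition but are optional, given the planned questionnaire summaries.
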